2.4.2 Known Potential Benefits

Both drugs have been demonstrated to reduce atopic eczema severity and improve quality of life (4, 5) However, there is equipoise with regard to which of the treatments is superior in terms of short-term efficacy (first primary outcome looks at the effectiveness of CyA vs MTX at 12 weeks) and more long-term disease control (secondary outcome is disease control during the six months follow up period).

Ciclosporin:

A systematic review of 11 clinical trials suggested that CyA is an efficacious treatment but that relapse is often seen, certainly when it is used only for short bursts of 2-3 months. The effectiveness of CyA was similar in children and adults, with good tolerability seen in younger patients with co-morbidities, even at the 5mg/kg/day dose (11). The open label RCT by Harper et al. suggested that more long-term treatment with CyA might result in disease remission, compared to short-term burst treatment(4), but none of the clinical trials included an observation period after treatment was stopped to assess the effect on natural history.

Methotrexate:

Although the evidence base for MTX is smaller than for CyA in severe atopic eczema, the RCT that compared methotrexate with azathioprine in adults (n=42, MTX vs AZA) (8), and the RCT in children (n=40, MTX vs CyA) (7) clearly demonstrated its positive effect on disease severity and quality of life, also underpinned by the three observational studies already discussed above.

19

IRAS: 182752

3 SELECTION OF CENTRES/CLINICIANS

Study centres will be initiated once all global (e.g. local R&D approval) and study-specific conditions (e.g. training requirements) have been met, and all necessary documents have been returned to CTRC. Initiation meetings will cover the requirements outlined in CTRC and KHP CTO SOPs.

3.1 Centre/Clinician inclusion criteria

Each participating centre (and Principal Investigator; PI) has been identified on the basis of:

- Having at least one consultant dermatologist with a specific interest in, and responsibility for supervision and management of patients with severe atopic eczema
- Showing enthusiasm to participate in the study
- Ensuring that sufficient time, staff and adequate facilities are available for the trial
- Providing information to all supporting staff members involved with the trial or with other elements of patient management
- Identifying that they will be able to recruit the required number of patients
- Acknowledging and agreeing to conform to the administrative and ethical requirements and responsibility of the study including adhering to GCP and other regulatory documentation
- Other important criteria are:
 - a. Local R&D approval/ Confirmation of capacity and capability
 - b. Completion and return of 'Signature and Delegation Log' to CTRC
 - c. Signed contract between site and sponsor
 - d. CTRC and KHP CTO green light process criteria are met

3.2 Centre/Clinician Exclusion Criteria

a. Not meeting the inclusion criteria listed above

4 TRIAL DESIGN

This study is a phase III, multi-centre randomised trial comparing methotrexate and ciclosporin. As per protocol trial treatment duration is for 36 weeks. Participants remain in the study for a total of 60 weeks post randomisation.

Participants will be randomised applying a ratio of 1:1.

5 STUDY POPULATION

5.1 Inclusion Criteria

- 1. Written informed consent for study participation obtained from the patient or parents / legal guardian, with assent as appropriate by the patient, depending on the level of understanding.
- 2. Aged 2-16 years at the time of the screening and randomisation visit
- 3. Diagnosis of severe recalcitrant atopic eczema
- 4. History of inadequate clinical response (in the opinion of the treating clinician) to potent topical corticosteroids on the body and moderate strength topical corticosteroids on the face.
- 5. An objective (o)-SCORAD severity score of at least 30
- 6. Participants must live within travelling distance of the recruiting centre
- 7. Females of childbearing potential and males, who are sexually active, must commit to consistent and correct use of an highly effective method of contraception (e.g. combined hormonal contraception, intrauterine device, physical barrier or abstinence) for the duration of the trial and for 6 months after the last dose of study drug.
 - a. Females of childbearing potential for this study are: Females, regardless of their age, with functioning ovaries and no documented impairment of oviductal or uterine function that would cause sterility. This category includes young females who have begun to menstruate, or females with oligomenorrhea.
- 8. Willingness to comply with study requirements
- 9. Baseline visit within 2 weeks of the screening visit

5.2 Exclusion Criteria

- 1. Serious underlying medical condition which in the opinion of the Investigator would compromise the safety of the patient.
- 2. Pregnant or nursing (lactating) females, where pregnancy is defined as the state of a female after conception and until the termination of gestation, confirmed by a positive hCG laboratory test.
- 3. Any active and/or chronic infection at screening or baseline (randomisation) visit that, based on the investigator's clinical assessment, makes the subject an unsuitable candidate for the study.
- 4. Presence of moderate to severe impaired renal function as indicated by clinically significantly abnormal creatinine (≥ 1.5 x upper normal limit (ULN) for age and sex) AND eGFR <60ml/min/1.73m² at screening visit.*
- 5. Clinical evidence of liver disease or liver injury at screening visit as indicated by abnormal liver function tests such as AST, ALT, GGT, alkaline phosphatase, or serum bilirubin (must not exceed 1.5 x the upper limit value of the normal range for age and sex).
- 6. Total WBC count <3x10⁹/L, or platelets <150x10⁹/L or neutrophils <1.5x10⁹/L or haemoglobin <8.5 g/L at screening visit.
- 7. Blood pressure values > 95th percentile for age and sex at screening *and* baseline visit. **
- 8. Received systemic cortico-steroids within 14 days prior to screening visit and 28 days of baseline visit.
- 9. Received phototherapy within 4 weeks prior to screening visit and 6 weeks of the baseline visit.
- 10. Previous exposure to any biologic agents or systemic immuno-suppressive therapy, except for oral corticosteroids (CS) for acute flare management.
- 11. Concomitant use of disease-modifying and/or immunosuppressive drugs.
- 12. Received live vaccines within 4 weeks prior to baseline visit.

- 13. Radiology report of abnormal chest x-ray at the screening visit (at the discretion of the PI/medically qualified physician see section 7.1 for further details)
- 14. Receiving treatment with medicines that are substrates for the multidrug efflux transporter P-glycoprotein or the organic anion transporter proteins (OATP) for which elevated plasma concentrations are associated with serious and/or life-threatening events; this includes bosentan, dabigatran etexilate and aliskiren.
- 15. Receiving treatment with products containing *Hypericum perforatum* (St. John's wort)
- 16. Receiving oral treatment with tacrolimus
- 17. Receiving oral treatment with everolimus and sirolimus
- 18. Receiving oral treatment with lercanidipine
- 19. Currently participating in a conflicting study or participation in a clinical study involving a medicinal product in the last 28 days or less than 5 half-lives of the medicinal product prior to the screening visit.
- 20. Known hypersensitivity to methotrexate or ciclosporin products.
- 21. Insufficient understanding of the trial by the patient and/or parent/guardian.
- *Please ensure the following formula is used for calculating eGFR: eGFR = height (cm) x 40/plasma creatinine (micromol/l)
- ** If an accurate blood pressure reading is unobtainable (e.g. due the patient being distressed), the patient's GP may be approached in order to obtain an accurate reading if a blood pressure measurement has been carried out within 4 weeks of the screening and baseline visit. A community nurse may also carry out a blood pressure measurement at the patient's home to confirm eligibility and also during the follow up visits. Without an accurate blood pressure measurement below the 95th centile of systolic BP for age and sex, a patient cannot be randomised into the trial.

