As for MTX, gastrointestinal disturbance, in particular nausea, liver function abnormalities and bone-marrow suppression are the main potential side effects, but the medication is well tolerated in the majority of cases and considered safe in the long-term, partly based on the extensive rheumatology and gastroenterology experience in children, using similar if not higher doses for longer periods of time and often in combination with biologics (4, 5, 20-23). In addition, the only RCT using MTX in children with severe atopic eczema over a 12 week period, the following adverse events were recorded: nausea/vomiting (4/20), abdominal pain (1/20), glossitis/oral ulceration (4/20), diarrhoea (5/20), pancytopenia (1/20), anaemia (6/20), leukopenia (2/20), abnormal liver function (5/20), abnormal renal function (1/20), fatique (6/20), headache (3/20), and flu-like symptoms (1/20). This overall favourable side effect profile has been confirmed by three observational studies, involving a total of 102 paediatric patients with treatment durations of up to 38 months (24-26). We are performing safety bloods after the initial test dose for MTX to capture rare idiosyncratic reactions early and review participants in both study arms with safety bloods and enquiry about adverse events fortnightly for the first month, then monthly until week 12 and then eight-weekly, while on treatment, in keeping with the American Academy of Dermatology guidelines for the use of these systemic agents in children with severe atopic eczema(27). Patients are also encouraged to contact the study team in case of any concerns about drug adverse reactions

between study visits. In addition, all potential participants and their parents will be informed about common and rare serious side effects in the Patient Information Leaflets and also instructed to contact the study team/seek medical advice straight away if any of the following occur:

Methotrexate:

- Infections, including fever (temperature above 38°C), chills, sore throat or chicken pox
- Skin rash, changes in nail or skin colour, or skin ulcers
- Jaundice
- Bleeding gums, unexpected bruising or bleeding that doesn't stop as quickly as normal
- Melaena
- Chest pain, difficulty breathing or chronic dry cough
- Severe and continuing diarrhoea, vomiting or stomach pains

Ciclosporin:

- Infections, including fever (temperature above 38°C), chills, sore throat or chicken pox
- Unusual bleeding that is difficult to stop
- Severe bruising

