8.3 Procedures for Assessing Safety

The following safety bloods and investigations will be performed:

- a. Safety blood profiles (full blood count, renal function and liver function) will be taken at screening, 2, 4, 8, 12, 20, 28, 36 and 60 weeks. Lipids will also be assessed at screening and week 4 as part of the safety blood profile. Safety bloods will also be taken at week 1 for the methotrexate arm. If it is not possible to obtain a safety blood sample (e.g. insufficient sample, participant refusal) at their visit, the remaining trial procedures can be carried out as normal and the patient can continue in the trial. However, the participant should be advised to temporarily stop trial treatment, until further advice is sought. The CTU should be contacted with the following information:
 - · Details of which safety blood values are missing
 - Date started treatment
 - Date and reason of any dose changes previously required
 - Details of any previous blood samples that had safety implications
 - Date of next scheduled visit

CTU will then liaise with CI (or delegate) and sponsor and will advise the site regarding the necessity to arrange an unscheduled visit to obtain missing safety assessment/s and when to reintroduce trial treatment. If a participant is not able to comply with the requested measures then permanent discontinuation of trial treatment may be considered, though in these circumstance the participant will be asked to continue in the study for follow-up purposes.

Please note, the above process does not apply to safety bloods taken at week 1 for the methotrexate arm, as this sample must be taken.

- b. BP will be taken at baseline, 2, 4, 8, 12, 20, 28, 36 and 60 weeks
- c. Chest X-Ray in those at risk of TB (discretion of local PI/medically qualified physician) at screening visit
- d. Physical examination will be carried out at each visit (except at the screening visit).

An Independent Data and Safety Monitoring Committee (IDSMC) will be constituted and will monitor adverse events and patient safety during the trial. Data on adverse events, including severity, seriousness, and expectedness as part of pharmacovigilance will be recorded at each follow-up visit and communicated to the CTRC. Requirements for pharmacovigilance reporting is detailed fully in Section 10 (Pharmacovigilance).

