18.3 Version 4.0 17/10/2016

Page number	Section	Change made		
Front page	NA	EME logo removed		
Front page	NA	Addition of ISRCTN number added		
Page 5	NA	Contact details for the KCL Bio Bank amended		
Page 11	NA	Child Health Utility – Nine Dimensions added to Glossary		
Page 12	1	Addition of REC number to protocol summary		
Page 12	1	Addition of oral solution to intervention section		
Page 12	1	Addition of CHU-9D questionnaire used to assess cost effectiveness of CyA vs MYA		
Page 21	3.1	Addition of confirmation of capacity and capability as part of centre inclusion criteria		
Page 23	5.1	Inclusion 4clarification of inadequate clinical response to topical corticosteroids		
Page 23	5.1	Inclusion 7 – addition of highly effective contraception including examples		
Page 23	5.1	Inclusion 9 – deletion of criteria as patient no longer required to swallow tablets/capsules as oral solutions are available		
Page 23	5.2	Exclusion 4 – clarification that values for both creatinine and eGFR are required to assess renal function		
Page 23	5.2	Exclusion 6 – unit measurement for haemoglobin amended		
Page 23	5.2	Exclusion 7 – information on blood pressure measurement taken by local GP or community nurse if unobtainable at screening or baseline visits added.		
Page 24	5.2	Exclusion 13 – addition that chest x-rays can be requested by the discretion of 'medically qualified physician'		
Page 24	5.2	Exclusion 21 – addition of 'patient and/or parent/guardian'		
Page 25	6.1	Further details added to clarify that consent and the screening visit can be carried out on the same day		
Page 25	6.1	Screening log amended to 'Consent & Eligibility log'		
Page 25	6.2	Detail added to clarify that data from clinical assessments carried out prior to consent for routine clinical purposes can be used for trial eligibility		
Page 26	6.3	Addition of safety bloods collected prior to screening visit can be used to assess eligibility at baseline visit		
Page 26	6.3	FLG genotyping sample collected at baseline visit		
Page 27	6.4.2	Removal of any reference to the blinded assessor being a research nurse as the blinded assessment can be carried out by an independent member of the research team who has no direct involvement or contact with trial patient		
Page 29	6.5.3	Detail added that CTRC are to notify the laboratories if a patient has withdrawn from the trial and requested that their data not to be analysed and to be destroyed		

Page 30	7.1	Addition of Methotrexate and Ciclosporin oral solution			

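### Exclusion 6 prints the haemoglobin limit as 8.5 g/L (0.85 g/dL), a value no child at screening could fall below, so that part of the criterion excludes nobody

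*Protocol*

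**What the plan says.** Item 6 of Section 5.2 of the current protocol (v7.0) sets four haematology limits at screening: total white cells, platelets, neutrophils and haemoglobin. They are joined by 'or', so any one of them excludes the child. The last three read "platelets <150x10⁹/L or neutrophils <1.5x10⁹/L or haemoglobin <8.5 g/L at screening visit"; the part at issue is "or haemoglobin <8.5 g/L at screening visit".

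The haemoglobin value comes from the full blood count at the screening visit (Section 8.3): "Safety blood profiles (full blood count, renal function and liver function) will be taken at screening".

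The protocol gives a reason to care about blood counts. For methotrexate, Section 2.4.1 states that gastrointestinal disturbance, "liver function abnormalities and bone-marrow suppression are the main potential side effects".

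The amendment log for version 4.0 (Section 18.3) has a line on this item: "Exclusion 6 – unit measurement for haemoglobin amended". It names neither the old unit nor the new one.

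**The concern.** A haemoglobin of 8.5 is a sensible exclusion limit in g/dL and a meaningless one in g/L. With the printed unit the limit lies below any value a screened child could have, so the haemoglobin part of item 6 does no work. The number fits one unit and the text gives another, which points to a drafting error and not to a lenient threshold chosen on purpose.

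What is at stake is entry safety. Both trial drugs can lower blood counts. In the paediatric trial of methotrexate against ciclosporin that Section 2.4.1 summarises, anaemia was recorded in 6 of 20 children on methotrexate and 4 of 20 on ciclosporin, and pancytopenia in 1 of 20 and 3 of 20, over 12 weeks. This trial treats for 36 weeks. A child who starts with severe anaemia has less reserve, and the written criterion does not keep that child out.

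**Working it through.** **Inputs**

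- Printed limit: haemoglobin below 8.5 g/L (Section 5.2, item 6).
- Conversion: 1 g/dL = 10 g/L.
- Assumption: the protocol gives no haemoglobin reference range. I take 50 to 180 g/L (5 to 18 g/dL) as a wide range for a child attending an outpatient clinic, from severe anaemia to high normal.

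**Step 1: the printed limit in the other unit.** 8.5 g/L ÷ 10 = 0.85 g/dL.

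**Step 2: can it be met?** The lowest value in the assumed range is 50 g/L, and 50 ÷ 8.5 = 5.9. The printed limit is therefore about one sixth of the lowest plausible value. The answer does not depend on where the lower end of the range is put, so long as it is above 8.5 g/L.

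**Step 3: the limit evidently meant.** 8.5 g/dL × 10 = 85 g/L. Ratio of intended to printed limit: 85 ÷ 8.5 = 10.

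**Step 4: who is treated differently.** Any value from 8.5 g/L up to just under 85 g/L passes the printed rule and fails the intended one:

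| Haemoglobin | Printed rule (<8.5 g/L) | Intended rule (<85 g/L) |
|---|---|---|
| 50 g/L | not excluded | excluded |
| 60 g/L | not excluded | excluded |
| 80 g/L | not excluded | excluded |
| 90 g/L | not excluded | not excluded |

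For the child at 60 g/L: 60 ÷ 8.5 = 7.06, so about seven times the printed limit; (85 − 60) ÷ 85 = 29.4%, so well below the intended one.

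**Step 5: is there a correct limit elsewhere?**

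- The eligibility summary in Section 1 has no haemoglobin limit.
- The dose-modification tables (Table 5 for ciclosporin, Table 8 for methotrexate) have action levels for platelets (<100x10⁹/L) and neutrophils (<1.5x10⁹/L), but no haemoglobin row.

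Item 6 is thus the only numeric haemoglobin limit in the protocol, and nothing corrects it. The missing row in the two tables is not a second fault; it only shows that there is no alternative figure to fall back on.

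**Step 6: could the unit have been misread from the PDF?** The neighbouring units on the same line read cleanly. The version 4.0 log shows that this unit was edited at some point, which would fit a change of unit without rescaling the number. But the log gives neither unit, so it would equally fit a change to g/dL with a letter lost in reading. A lost 'd' is possible but not likely, and a look at the signed protocol settles it.

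**The case against.** The best case on the other side accepts that the text is wrong and argues that it hardly matters.

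- **The slip is obvious.** A limit incompatible with life will be recognised by any clinician who reads blood counts. A wrong but plausible number would be more dangerous, because nobody would question it.
- **Other safeguards exist at entry.** Exclusion 1 covers a "Serious underlying medical condition which in the opinion of the Investigator would compromise the safety of the patient". A full blood count is taken at screening, and Section 6.3 requires a medically qualified physician to confirm eligibility before randomisation.
- **Monitoring follows.** Under Section 8.3, full blood counts are repeated at weeks 2, 4, 8, 12, 20, 28, 36 and 60. The methotrexate arm also has a mandatory week 1 sample, and Section 7.3.3 allows the full dose only if the safety bloods are acceptable. A missed sample at the other visits leads to advice to pause treatment. Section 6.5.2 allows discontinuation for toxicity.
- **No harm is shown.** The document does not show that any anaemic child was enrolled. If recruitment has closed, which the document does not say, an amendment protects nobody further.

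Most of this stands, and it limits how serious the point is. It does not remove the error. The safeguards at entry rest on judgement, and the physician's check is made against the written criteria. On those, a site that enrols a child at 60 g/L complies with item 6, while a site that excludes the child under item 6 departs from it. Monitoring on treatment addresses toxicity after exposure, not whether the child should have started. A numeric safety limit should not need each reader to correct it silently.

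**Conclusion.** The error is real and sits in the current text. The printed haemoglobin limit is one tenth of the figure evidently meant, and the haemoglobin part of exclusion 6 cannot exclude anyone in practice. The conclusion rests on two assumptions: that no screened child has a haemoglobin near 8.5 g/L, which is safe, and that 8.5 g/dL was the intended limit, which is very likely but for the clinical lead to confirm.

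It should be fixed, but its reach is limited. The other three limits in item 6 still work. The sample size, the type I error and both co-primary analyses do not change. How sites applied the criterion, and how many children it affected, cannot be learned from the protocol.

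**What to change.** 1. Have the clinical lead confirm the intended limit, and check the unit against the signed protocol.
2. Amend the last part of Section 5.2, item 6, to: haemoglobin <85 g/L (8.5 g/dL). Giving both units prevents the same slip from recurring.
3. Correct any eligibility form or checklist that copies the text.
4. List the screening haemoglobin of every randomised child against the confirmed limit, and report any value below it. This is worth doing even if recruitment has closed, because it shows whether the error had any consequence.

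The cost is a one-line correction and one listing from data already held. Neither the analysis nor the sample size changes.

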6 ENROLMENT, RANDOMISATION AND WITHDRAWAL

6.1 Recruitment and Screening

Participants will be identified by the clinical team at each centre via a search of the patient database/s either electronically or manually or clinic list review to find potentially eligible patients. At the routine clinic visit, the patient and/or parent/guardian will be asked whether they would be willing to participate in the study. A Patient Information Sheet and instructions on how to proceed if they are interested in taking part or finding out more about the study will be given to the patient and/or parent/guardian. They will be provided with a telephone number to contact the research nurse if they need to discuss or need further information. All patients and/or parent/guardian will be provided with a full explanation of the trial before obtaining informed written consent (see Section 11.3 for the consent procedure) at the screening visit.

The time taken from initial contact and provision of information to obtaining written consent should be sufficient to enable appropriate discussions with the patient / family about the trial, explanation of the protocol and procedures, and seeking formal consent.

A patient and/or parent/legal guardian should be provided with the study information during their outpatient appointment and may be approached for consent during this visit if considered appropriate. Where the patient and/or parent/legal guardian feel that they have adequate information regarding the trial and are happy to proceed then consent can be sought and screening assessments undertaken on the same day as initial contact and provision of information.

A 'Consent & Eligibility Log' will be maintained to record all the patients who attend dermatology clinics that have severe recalcitrant atopic eczema (in the opinion of the treating clinician). Patients will be recorded on the log regardless of whether they decide to participate in the study or are found ineligible to participate. Reasons for not being eligible will be recorded on the log. Reasons for declining to participate will be asked routinely but it will be made clear that they do not have to provide a reason unless happy to do so. The participating site will assign the patient a screening number for use on the study documentation, until randomisation number is allocated.

